7.2.2 Immune status assessments

Immune status will be assessed by the following end points:

- absolute lymphocyte count
- lymphocyte subset (B, T, and NK) analysis: the number of cells for each subset will be determined by fluorescence-activated cell sorter (FACS) using the following panel:
 - CD3+ (Mature T cells) Percent and Absolute
 - CD3+ CD8+ (Suppressor T Cells) Percent and Absolute
 - CD3+ CD4+ (Helper Cells) Percent and Absolute

- CD (16+56) + (NK Cells) Percent and Absolute
- CD19+ (B Cells) Percent and Absolute
- Absolute Lymphocytes (CD45+)
- %CD4 (Helper Cells)/% CD8 (Suppressor T Cells)
- Quantitative immunoglobulin (Ig) concentration (IgG, IgA, IgM).

The absolute values and the changes from baseline for all endpoints for immune status will be summarized by descriptive statistics for all time points. 95% CIs for the means will be calculated for each time point based on the normal distribution function for the actual values and the changes from baseline. Baseline for the STP 2279-002 transitioning subjects will be handled the same as for the biochemical assessments.

It is recommended that Investigators consider a measurement of immune response (PHA stimulation or equivalent). These data will be listed but not summarized.

7.2.3 Clinical status

Clinical status will be assessed through determination of the following:

- Infections will be determined and defined as either:
 - Clinically documented subjects with documented signs and symptoms of infection without positive microbiologic cultures
 - Microbiologically documented subjects with documented signs and symptoms of infection and with positive viral or bacterial cultures
- Hospitalizations incidence and duration of hospitalizations through completion of the study
- Growth height, weight and growth curve determinations through completion of the study (Note: this assessment should be done for subjects < 18 years of age)
- Overall survival through the end of the study

Infections will be extracted from the adverse event dataset as all reported adverse events where the question "Is this event an Infection?" is answered by "Yes" and the Classification is reported as "Clinically documented" or "Microbiologically documented". Events classified as "Unknown" will not be included in the analysis of the infections. However, events classified as Unknown will be included in the analysis of the adverse events as part of the safety analysis (see section 8.2). The following time periods will be analyzed:

1. The year prior to treatment start with Revcovi (study day -365 to -1)

- 2. From Treatment initiation until 1 year after treatment initiation with Revcovi (Study day 1 to 365)
- 3. From one to 2 years after treatment initiation with Revcovi (Study day 366 to 730).
- 4. From 2 to 3 years after treatment initiation with REVCOVI (Study days 731 to 1095)
- 5. From 3 to 4 years after treatment initiation with REVCOVI (Study days 1096 to 1461).
- 6. From 4 to 5 years after treatment initiation with REVCOVI (Study days 1462 to 1826).
- 7. From 5 to 6 years after treatment initiation with REVCOVI (Study days 1827 to 2191).
- 8. From 6 to 7 years after treatment initiation with REVCOVI (Study days 2192 to 2556).
- 9. From 7 to 8 years after treatment initiation with REVCOVI (Study days 2557 to 2921).
- 10. From 8 to 9 years after treatment initiation with REVCOVI (Study days 2922 to 3286).
- 11. At any time after treatment initiation with REVCOVI (Study day 1 onwards)

For the STP-2270-002 subjects, the observational period for infections and hospitalizations after treatment initiation starts at the first dose of REVCOVI in the CLI-06814AA1-01 study. Infections and hospitalizations occurring during the STP-2279-002 study will not be included in the summary tables for the CLI-06814AA1-01 study.

The time periods will be defined as follows:

The year prior to treatment start with Revcovi will be defined as study day -365 to study day -1. For subjects younger than 1 year of age at the time of treatment initiation with Revcovi, it will be defined as the time period from the date of birth until study day -1 (time period calculated as date of first dose of Revcovi - date of birth + 1 day).

The end date of the time periods 1, 2, 3, 4, 5, 6, 7, 8, and 9 years after treatment initiation of Revcovi, respectively, will be defined as the earliest of the following events:

- End of time period (study day 365, 730, 1095, 1461, 1826, 2191, 2556, 2921, and 3286 respectively)
- Last date of treatment with Revcovi + 30 days
- Study completion date
- Study discontinuation date

- Date of death
- Date of transplantation

Infections occurring more than 30 days after the last dose of Revcovi will not be included in the calculation of the incidence rates, but will be included in the data listings and flagged.

The following analyses will be performed for the infections for each time period defined above:

- Number of events, number and percentages of affected subjects by SOC and PT. The denominator for the calculation of the percentages is the number of subjects with an observational period of 1 day or more in the respective analysis period, i.e. if the end date as defined above is not prior to the start date of the respective analysis period.
- Incidence rate of infections (in number of infections per year). The incidence rate will be based on the number of events, not on the number of affected subjects.
 95% CIs will be calculated for the incidence rates by the method of Ulm, assuming a Poisson distribution. The total observational period will be defined as the sum of the time periods for each subject from the start until the end date of the respective time period as defined above (end date start date + 1 day).

For both analyses, the infections will be slotted to the analysis periods based on the onset date of the adverse event.

The number of hospitalizations will be analyzed similarly as the infections, i.e. number of hospitalizations, number and percentages of hospitalized subjects, incidence rates of hospitalizations for the time periods described above. The duration of hospitalizations will be described by descriptive statistics for continuous variables based on the number of hospitalizations. Subjects who are hospitalized in one analysis period and discharged from the hospital in the subsequent analysis period will be counted for the full hospitalization period (i.e. from admission to discharge) in the analysis period where they were hospitalized. All hospitalizations will also be presented in a data listing.

For subjects <18 years of age, height-for age and weight-for age and for patients between 24 months and 18 years of age, BMI-for age will be presented by z-scores at baseline and each intermediate collection time-point. Z-scores will be calculated programmatically based on reported age, gender, height and weight.¹ Z-scores and changes from baseline of z-scores to each visit (at which height and weight are assessed) will be summarized using descriptive statistics.

¹ http://www.cdc.gov/nccdphp/dnpao/growthcharts/resources/sas.htm

Overall survival will be analyzed by a Kaplan-Meier analysis. Kaplan-Meier survival curves will be plotted by subject status. Subjects who are alive at the end of the observational period will be counted as a censored observation. Observational period is the time from initiation of Revcovi until the date of study completion or study discontinuation (calculated as: date of study completion or study discontinuation – date of treatment initiation + 1 day) or from treatment initiation until the date of death, for subjects who die (calculated as date of death – date of treatment initiation + 1 day). Date of study completion or date of study discontinuation will be used as reported on the Patient Disposition page in the eCRF. For subjects transitioning from the STP-2279-002 study, overall survival will be calculated based on the date of the first dose of Revcovi in the STP-2279-002 study. If it is known that the subject died, but the date of death is unknown, it will be assumed that the subject died the day after their last assessment (whatever has been entered as last available date to the database, e.g. date of laboratory value, onset or resolution date of an AE, date of study discontinuation).

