10.3 History and Baseline Characteristics

The following history and demographic data will be collected:

- Demographics age, gender, race, and ethnicity
- Disease background and history:
 - Date of diagnosis
 - Prior treatments for severe combined immunodeficiency, including dates and results
 - History of hospitalizations and infectious complications over the past year
 - Other significant disease-related medical history
- Medical History in addition to the disease background and history, a complete evaluation of history of disorders of the following systems cardiovascular, pulmonary, gastrointestinal, urologic, hematologic, neurologic, ophthalmologic, otolaryngeal, musculoskeletal, endocrine, and psychosocial. Note: any medications being taken for active conditions should be included in the medication history, while prior surgical procedures and allergies to medications, including medication and reaction should be included in the medication history.
- Medication History all prescription and non-prescription medications (including blood products, use of vitamins, supplements and herbal remedies) taken since the first dose of Revcovi will be recorded. Information recorded includes the medication name, dose, dose regimen, route of administration, start and stop (if applicable) dates, and indication for use. Note: if a product is being taken for the prevention of a condition, "prophylaxis for" or "prevention of" should be included in the description of indication.

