11.1 Enrollment

Subjects who fulfill all of the inclusion criteria and none of the exclusion criteria may be enrolled into the study. The date of ICF signature is the date of enrollment into the registry.

The following evaluations should be performed or collected retrospectively (if available) before starting Revcovi unless otherwise indicated.

- Informed assent/consent
- Demographics
- Medical history and baseline characteristics (including ADA-mutation results, if available)

- Assessment of infectious complications and hospitalizations within the past 12 months
- Concomitant medications/procedures
- Physical examination (including height and weight) from 1 year prior to start of Revcovi treatment
- Vital signs
- Safety laboratory assessments: hematology, serum chemistry, urinalysis (if available)
- Immune Function (if available)
- B-/T-/NK-lymphocyte subset
- Trough plasma ADA activity and erythrocyte dAXP
- Quantitative immunoglobulins
- Immune Function analyses (response to PHA, pneumococcal vaccine or equivalent)
- Immunogenicity Revcovi antibody titers (i.e., neutralizing and binding antibodies) and anti-PEG antibodies (only if indicated)
- Quality of Life assessments

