12 ADVERSE EVENTS

12.1 Assessment Period

AEs are assessed from the time the subject receives their initial dose of Revcovi during the CLI-06814AA1-01 registry through 4 weeks following the last dose. Subjects undergoing HSCT or HSCGT will be followed one month and again at 6 months after last Revcovi dose to assess AEs and survival.

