12.2 Definitions

12.2.1 Adverse Event

An AE is any untoward medical occurrence associated with the use of a drug in humans, whether or not considered drug related. An AE can therefore be any unfavorable and unintended sign (including an abnormal laboratory finding, for example), symptom, or disease temporally associated with the use of a drug and does not imply any judgment about causality.

An untoward medical event which occurs outside the period of follow-up as defined in the protocol is not considered an AE. Worsening of a medical condition for which the efficacy of the drug is being evaluated is not considered an AE.

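### The SAP takes infections in the year before Revcovi only from the AE dataset, while the protocol starts AEs at the first registry dose; unless look-back infections are also entered as AEs, the pre-treatment rate is understated

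*SAP*

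**What the plan says.** **SAP 7.2.3 (Clinical status).** The event source is stated once, for all periods: "Infections will be extracted from the adverse event dataset as all reported adverse events where the question" about infection is answered yes and the classification is clinically or microbiologically documented. Events classified as unknown "will not be included in the analysis of the infections". The first period is "The year prior to treatment start with Revcovi (study day -365 to -1"), or from birth for subjects under one year old. "The following analyses will be performed for the infections for each time period defined above": event counts, affected subjects, and an events-per-year rate with a 95% Poisson interval by the method of Ulm. Events are placed by AE onset date. Person-time is summed over subjects, with no condition that a subject's prior history was obtained.

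**Protocol 12.1 and 12.2.1.** "AEs are assessed from the time the subject receives their initial dose of Revcovi during the CLI-06814AA1-01 registry", and "An untoward medical event which occurs outside the period of follow-up as defined in the protocol is not considered an AE". In both schedules (Appendices 1 and 2) the adverse-event row has no mark at enrolment.

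**Protocol 10.3 and 11.1.** Infections before treatment are collected under disease background, as "History of hospitalizations and infectious complications over the past year", and among the enrolment evaluations, as "Assessment of infectious complications and hospitalizations within the past 12 months".

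**What the SAP does with history.** Section 6.5 lists medical history without summarising it. The disease-background items in 6.4 do not include infection history. Section 7.1 declares no change from the protocol's efficacy analysis.

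**The concern.** Numerator and denominator of the pre-treatment rate follow different rules. The denominator counts every subject's prior year. The numerator counts only events in a dataset that, under the protocol, begins at the first registry dose. A site applying protocol 12.1 as written would record a prior-year infection as history, where the SAP's extraction does not look.

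The analysis is descriptive, so the displayed rates and intervals are the result. SAP 8.2 treats infections as an efficacy measure, and protocol 13.2.3 has subjects serve as their own controls where appropriate. Readers will therefore set the pre-treatment rate beside the on-treatment rates. If the former is too low, infections appear to rise, or to fall less than they did, after Revcovi starts. That could hide a benefit or suggest a safety signal that is not there.

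**Working it through.** The documents state no infection rate, event count or sample size, so there is no planned figure to reproduce. The check has three parts.

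**1. Denominator.** Using the SAP's rule of end − start + 1:

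- Pre-treatment period: −1 − (−365) + 1 = 365 days.
- First treatment year: 365 − 1 + 1 = 365 days.

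A subject aged one year or more contributes a full pre-treatment year whether or not any prior infection reaches the AE dataset. Each missed event therefore lowers the rate in direct proportion.

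**2. Effect of incomplete capture.** Let c be the fraction of true prior-year infections entered as classified AEs, D the true number and PY the person-years.

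- Reported rate = c·D/PY, so the relative understatement is 1 − c.
- Reported post/pre ratio = true ratio/c, if on-treatment capture is complete.
- With d = c·D events, the exact Poisson 95% limits are χ²(0.025; 2d)/(2·PY) and χ²(0.975; 2d + 2)/(2·PY).

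Assumed inputs, for illustration only: 20 subjects, a full prior year each, a true rate of 1.0 per year (D = 20) and a true post/pre ratio of 0.5. With 365.25 days per year (12 × the 30.4375 days per month in SAP 8.7), PY = 20 × 365/365.25 = 19.99.

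| Capture c | Events d | Reported rate per year (95% CI) | Reported post/pre ratio |
|---|---|---|---|
| 100% | 20 | 1.00 (0.61–1.55) | 0.50 |
| 75% | 15 | 0.75 (0.42–1.24) | 0.67 |
| 50% | 10 | 0.50 (0.24–0.92) | 1.0 |
| 25% | 5 | 0.25 (0.08–0.58) | 2.0 |
| 0% | 0 | 0.00 (0.00–0.18) | undefined |

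For example, at c = 0.5 the ratio is 0.5/0.5 = 1.0. In this example, at 50% capture or less the interval excludes the assumed true rate of 1.0, because it reflects Poisson variation and not missed events. A true rate of 2.0 doubles the event counts but leaves the ratio column unchanged, since the ratio depends only on c.

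**3. STP-2279-002 subjects.** SAP 13.2 and 13.3 set their Study Day 1 at the first Revcovi dose in the earlier study, so their day -365 to -1 lies before that study. A 12-month look-back taken at registry enrolment covers a later year. For infections, SAP 7.2.3 moves only their post-treatment start to the first registry dose. It neither removes their pre-treatment person-time nor names a source for those events.

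**The case against.** The best reply is that the SAP's authors evidently expected pre-drug events in the AE dataset:

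- SAP 8.2 names infections as a class recorded in the eCRF, separately from Revcovi-related events, and gives no start date.
- SAP 13.5 defines a pre-treatment AE category.
- SAP 14 imputes AE onsets that fall in a month or year before first drug, and flags non-treatment-emergent AEs in listings.
- The AE page carries its own infection question and classification.
- The SAP was written after an interim analysis that presented infections, so the authors had seen data.
- Neither document describes a separate infection-history form.

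This stands to the extent that a reader who infers that the rate **is** undercounted goes further than the documents allow. Look-back infections may well be keyed on the AE page. But nothing requires it. The pre-treatment category and the imputation rules are tied to the registry start of Revcovi, so they would also be needed for AEs that STP-2279-002 subjects carry over from the earlier study, a case SAP 8.2 describes. Dropping events of unknown classification could add to the loss, if retrospective infections are harder to classify.

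Two further inferences are tempting and unsupported:

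- A reader might think that infections between a commercial start of Revcovi and enrolment are lost in the same way. Protocol 7.1 asks for retrospective collection under the suggested schedule, which marks AEs at every post-enrolment visit, and protocol 14.7.1 defines data-entry periods from the Revcovi start date.
- A reader might call this the sole within-subject efficacy contrast for infections. The plan has no formal contrast at all, only separate rates per period, and successive treatment years can also be compared within subjects.

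Finally, the SAP cites protocol Version 4.0 and the protocol at hand is Version 5.0. Section 12.1 may have read differently in the earlier version. That does not settle the source under the current text.

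**Conclusion.** The concern holds conditionally. SAP 7.2.3 and protocol 12.1/12.2.1 are not reconciled. Followed as written, they leave prior-year infections outside the dataset that supplies the pre-treatment numerator while the person-time is counted in full. Unless look-back infections are also entered as AEs, the pre-treatment rate is understated by 1 − c and the descriptive before/after reading is biased against Revcovi. An undercount of this kind could not create a false claim of benefit.

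The documents give neither c nor any event count, so they establish neither that an undercount exists nor its size. The figures above rest on assumed subject numbers and rates and on complete on-treatment capture. The STP-2279-002 gap needs separate handling: even full entry of an enrolment look-back would not cover the year that the SAP assigns to those subjects.

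**What to change.** In SAP 7.2.3:

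1. Name the eCRF page that supplies infections for the pre-treatment period. Use the 12-month enrolment look-back, or the AE page if it is confirmed that look-back infections are entered there.
2. Code and classify these infections in the same way as on-treatment infections, and state how they are dated.
3. Count pre-treatment person-time only for subjects with a completed look-back covering day -365 to -1 (or birth to day -1). This excludes STP-2279-002 subjects if the year before that study was not collected.
4. If these conditions cannot be met, list prior infections without a rate.

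The cost is SAP wording, some extra data handling and a smaller pre-treatment denominator. The data presented at the interim analysis allow a quick check of whether pre-treatment infections are in the AE dataset. If they are, one sentence settles the source, and the person-time restriction is still needed.

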10.8 Clinical Status

10.8.1 Infections

Subjects suspected of having an infection should have signs and symptoms of the suspected infection evaluated. Appropriate cultures should be obtained based upon clinical presentation.

All infections will be classified by the Investigator as clinically or microbiologically documented as described below:

- Clinically documented subjects with documented signs and symptoms of infection without positive cultures
- Microbiologically documented subjects with documented signs and symptoms of infection and with positive cultures

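### Infections classed Unknown leave the counts and rates while their person-time stays, so rates are understated by the Unknown share and may not be comparable between periods

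*SAP*

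**What the plan says.** SAP 7.2.3 draws infections from the adverse event data by two conditions: the eCRF infection question is answered Yes, and the class is recorded as clinically or microbiologically documented. Events classed Unknown "will not be included in the analysis of the infections". The same paragraph adds that "events classified as Unknown will be included in the analysis of the adverse events as part of the safety analysis".

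The incidence rate in SAP 7.2.3 is events divided by total observation time, with a Poisson interval by the method of Ulm. Observation time is summed over subjects from the start to the end of each period. Nothing is deducted for excluded events. The periods are the year before Revcovi, each year after its start, and all time after its start.

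Protocol 10.8.1 provides for no third category: "All infections will be classified by the Investigator as clinically or microbiologically documented as described below". Protocol 13.2.3.6 plans the number of events in those two classes.

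The class definitions do not agree. In SAP 7.2.3 the clinical class is "subjects with documented signs and symptoms of infection without positive microbiologic cultures" and the microbiological class is "subjects with documented signs and symptoms of infection and with positive viral or bacterial cultures". SAP 2.2 and protocol 6.3 use the same narrow wording. Protocol 10.8.1, which tells the investigator how to classify, asks only for a positive culture of any kind.

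**The concern.** An event that the site has reported as an infection is left out because one descriptive field is Unknown. Read literally, the two conditions also drop an event whose class is blank. The subject's time at risk stays in the denominator. A subject whose only infections in a period are Unknown still counts in the percentage denominator, but as unaffected.

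The table invites comparison of the year before Revcovi with the years after. The earlier year comes from a 12-month look-back at enrollment (protocol 10.3 and 11.1), so the completeness of the class could well differ from later years. A difference in record quality could then look like a change in infection incidence.

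The definitions add a second route to Unknown. Under the SAP wording, a culture-positive fungal infection is not clinical, because a culture is positive, and not microbiological, because the culture is neither viral nor bacterial. The protocol synopsis includes opportunistic infections, and protocol 5.3.2 lists a fungal skin infection and oral candidiasis in an earlier Revcovi study, without culture status.

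**Working it through.** The documents state no infection rate, Unknown share or sample size, so there is no figure of the plan to reproduce. The shares and counts below are assumptions that show scale.

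**Rate within one period.** Let R be the rate of all events answered Yes and u the share of them classed Unknown. The numerator loses u and the denominator is unchanged:

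counted rate = R × (1 − u)

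Assume 40 such events in 20 person-years, with exact Poisson 95% intervals:

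| Unknown share | Events counted | Rate per year (95% CI) |
|---|---|---|
| 0% | 40 | 2.00 (1.43 to 2.72) |
| 5% | 38 | 1.90 (1.34 to 2.61) |
| 10% | 36 | 1.80 (1.26 to 2.49) |
| 20% | 32 | 1.60 (1.09 to 2.26) |
| 30% | 28 | 1.40 (0.93 to 2.02) |
| 40% | 24 | 1.20 (0.77 to 1.79) |

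The interval shifts with the estimate, so it gives no sign that events were left out.

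**Comparison of two periods.** If the true rates are equal, the apparent ratio is

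after/before = (1 − u_after) / (1 − u_before)

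| Unknown before | Unknown after | Apparent ratio |
|---|---|---|
| 30% | 10% | 0.90/0.70 = 1.29 |
| 10% | 30% | 0.70/0.90 = 0.78 |
| 20% | 5% | 0.95/0.80 = 1.19 |
| 10% | 20% | 0.80/0.90 = 0.89 |
| equal shares | | 1.00 |

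More Unknown before treatment makes Revcovi look worse; more Unknown after makes it look better.

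**Where the excluded events can still be seen.** SAP 14 limits AE summary tables to treatment-emergent events, and SAP 13.5 classes events before the Revcovi start date in this study as pre-treatment. An Unknown infection in the year before treatment therefore reaches a listing and no table. For treatment-emergent events, SAP 8.2 tabulates by system organ class and preferred term and gives yearly rates for all AEs and all SAEs, but not for infections. No planned table gives an infection rate that includes Unknown events, for any period.

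**Handling of other incomplete fields.** In SAP 8.2 a missing relationship to study drug is counted as related, and an event with no severity grade goes into a Missing category. Both rules keep the event. The infection rule removes it from the endpoint.

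**The case against.** The strongest reply is that the two-class count is the protocol's own endpoint. Protocol 13.2.3.6 names those two classes, and both require documented signs and symptoms. Counting every Yes is a broader measure with weaker evidence behind some events. That stands, and it is why the two-class rate should be kept, not replaced. It does not explain why the broader count should be shown nowhere.

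The exclusion is also stated openly, and treatment-emergent Unknown events remain in the AE tables. That is true, but it does not cover the year before treatment.

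The plan is descriptive. It gives a rate and interval for each period and no rate ratio, so 1.29 and 0.78 are not planned outputs. They show what a reader setting the rows side by side could be led to see. Nor is retrospective capture confined to the year before treatment: under protocol 7.1, subjects who began Revcovi before enrollment have on-treatment data collected retrospectively too. This weakens any assumption about which period has more Unknown events.

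A reader might infer that culture-positive fungal infections are lost from the analysis. The documents do not show that. Protocol 10.8.1 accepts any positive culture, and the SAP selects on the class recorded in the eCRF, without applying "with positive viral or bacterial cultures" as a filter. Such an event is lost only if the site records neither class. What stands is a conflict between definitions.

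**Conclusion.** The point holds in conditional form. If events answered Yes are classed Unknown, each rate falls short of the rate of all reported infections by exactly the Unknown share, and comparison between periods is distorted when the shares differ. With no Unknown events the effect is nil; with equal shares the levels are low but the ratio is unaffected. The shares used above are assumptions, so neither size nor direction can be stated. The plan as written would also leave a reader of the tables unable to tell which case applies.

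Three stronger readings are not supported. One is that the rates are in fact too low or favour Revcovi: no Unknown count is given, and more Unknown events in the look-back year would work against the drug. Another is that the excluded events are confirmed infections: the SAP requires only a Yes answer. The third is that infection incidence is the main efficacy measure: SAP 7.2.3 and protocol 13.2.3.6 list it beside hospitalizations, growth and survival without ranking.

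**What to change.** In SAP 7.2.3, for each period, report the number of events, affected subjects and incidence rate for all events with the infection question answered Yes. Under that line give rows for clinically documented, microbiologically documented, and Unknown or missing class. Keep the two-class rate alongside as the measure that follows protocol 13.2.3.6, and record the added rate in SAP 7.1, which now declares no changes to the planned efficacy analysis. Readers can then see the Unknown share by period.

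Separately, reconcile the culture wording in protocol 6.3 and SAP 2.2 and 7.2.3 with protocol 10.8.1, so that a culture-positive fungal infection has a class. Say also how Unknown arises, since protocol 10.8.1 does not provide for it.

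The cost is small. The SAP rule already relies on both eCRF fields, so no new data are needed. The SAP change is wording and a few table rows; the protocol 6.3 wording needs a protocol amendment. The downside is that the all-infection rate includes some less well documented events, which stay visible in their own row.
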